#### •Registry reports (*e.g.* HES)

Periodic reports will be sourced from national registries/databases. Identified SAEs will be entered to the trial database by Cambridge study team.

The Cambridge study team receive immediate notification by email that an SAE has been recorded in the trial eCRF and will ensure the event is reported within the appropriate timelines (see appendix 2 – Modified safety reporting).

In the event that a participant contacts the study staff and immediate eCRF data entry is not possible an SAE form can be faxed or emailed to the Cambridge study team to ensure reporting timelines can be met.

For serious adverse events reported via direct participant contact to site staff, the 24 hour clock starts at the time of contact. The site will enter the event via the eCRF immediately.

For serious adverse events identified by questionnaires and national registries/databases the 24 hour clock starts at the time data review identifies a reportable event

# 12.6 Reporting of Suspected Unexpected Serious Adverse Reactions (SUSARs)

All suspected adverse reactions related to an investigational medicinal product (the tested IMP and comparators) which occur in the concerned study, and that are both unexpected and serious (SUSARs) are subject to expedited reporting. Please see section 12. 2 for the Reference Safety Information to be used in this study. All SUSARS will be reported in an expedited manner.

# 12.6.1 Who should report and whom to report to?

The Sponsor delegates the responsibility of notification of SUSARs to the Chief Investigator.

The Chief Investigator must report all the relevant safety information previously

described, to the:

•Sponsor,

•Competent authorities in the concerned member states (eg MHRA) •Ethics Committee in the concerned member states

The Chief Investigator shall inform all investigators concerned of relevant information about SUSARs that could adversely affect the safety of participants.

#### 12.6.1When to report?

#### 12.6.1.1 Fatal or life-threatening SUSARs

All parties listed in 12.6.1 must be notified as soon as possible but no later than **7** calendar days after the GLINT team has first knowledge of the minimum criteria for expedited reporting.

In each case relevant follow-up information should be sought and a report completed as soon as possible. It should be communicated to all parties within an additional **8** calendar days.

#### 12.6.1.2Non fatal and non life-threatening SUSARs

All other SUSARs and safety issues must be reported to all parties listed in 11.7.1 as soon as possible but no later than **15 calendar days** after first knowledge of the minimum criteria for expedited reporting. Further relevant follow-up information should be given as soon as possible.

#### 12.6.2How to report?

#### 12.6.2.1 Minimum criteria for initial expedited reporting of SUSARs

Information on the final description and evaluation of an adverse reaction report may not be available within the required time frames for reporting. For regulatory purposes, initial expedited reports should be submitted within the time limits as soon as the minimum following criteria are met:

a) a suspected investigational medicinal product,

b) an identifiable subject (e.g. participant code number),

c) an adverse event assessed as serious and unexpected, and for which there is a reasonable suspected causal relationship,

d) an identifiable reporting source,

and, when available and applicable:

- a unique clinical trial identification (EudraCT number or in case of non-European Community trials the sponsor's protocol code number)

- a unique case identification (i.e. sponsor's case identification number).

#### 12.6.2.2 Follow-up reports of SUSARs

In case of incomplete information at the time of initial reporting, all the appropriate information for an adequate analysis of causality should be actively sought from the reporter or other available sources. Further available relevant information should be reported as follow-up reports.

In certain cases, it may be appropriate to conduct follow-up of the long-term outcome of a particular reaction.

#### 12.6.2.3 Format of the SUSARs reports

Electronic reporting is the expected method for expedited reporting of SUSARs to the competent authority. The format and content as defined by the competent authority

should be adhered to.

#### 12.7 Pregnancy Reporting

The occurrence of pregnancy in participants during the study should be reported to the Chief Investigator and the Sponsor within 14 days of notification.

Pregnancy is not considered an AE unless a negative or consequential outcome is recorded for the mother or child/foetus. If the outcome meets the serious criteria, this would be considered an SAE.

#### 13 Evaluation of Results (Definitions and response/evaluation of endpoints)

Study endpoints will be defined based on clinical standards, regulatory precedent, and historical trials. These definitions will be provided in an endpoint ascertainment manual for the Clinical Events Classification Committee (CEC). Participants and their GPs will be surveyed annually regarding procedures and hospitalisations which have taken place between study contacts. We may also conduct electronic READ code searches in participant GP records to search for relevant clinical outcomes. Medical records pertaining to hospitalisations and procedures of interest will be obtained and thoroughly reviewed in order to determine whether an event of significance has occurred. HES data will also be accessed to provide evidence for potential endpoints. This information will be collated and anonymised in an 'endpoint pack' and sent to the CEC for review.

Events included in the primary composite outcome, all-cause mortality, hospitalisations for heart failure and unstable angina, and coronary, cerebrovascular or peripheral revascularisations will be adjudicated by the CEC blinded to study treatment.

#### 14 Storage and Analysis of Samples

Samples will be collected for immediate and future biomarker measurements. Fresh blood samples will be sent to local NHS clinical biochemistry laboratories for the measurement of standard clinical blood tests. Additional research samples will be collected and stored for genetic and other biomarker work. The research samples will be stored in a -80°C freezer. All samples will be logged into a central database and will be stored at either access controlled local sites or in an off-site Human Tissue Authority licenced facility. All stored samples will be link anonymised.

#### 15 Statistics

#### 15.1 Statistical methods

Analysis of primary endpoint in the full study

The primary endpoint is a time-to-event variable indicating whether or not each participant experienced any of the following events as verified by the study endpoint committee: CV mortality, non-fatal myocardial infarction or non-fatal stroke. The number and percentage of individuals experiencing the endpoint will be presented, by randomised group, along with the median and inter-quartile range of the time to event/censoring. The cumulative incidence of the endpoint, by randomised group, will be estimated using the method described by Gooley [25] and plotted.

A Cox regression model, with time since randomisation as the underlying timescale, will be used to estimate the hazard ratio, 95% confidence interval and p-value for the comparison of the metformin group with the placebo group. The assumption of proportional hazards will be tested by including a parameter for randomised group x time interaction in the Cox regression model, as well as by checking Schoenfeld residuals, and using 2 standard graphical checks which will be described in the Statistical Analysis Plan. If these tests and graphical checks provide strong evidence against the proportional hazards assumption, then alternative modelling approaches will be considered; these will be outlined in the Statistical Analysis Plan.

Each of the individual components of the primary endpoint, i.e. CV mortality, non-fatal MI, and non-fatal stroke will be analysed separately using the same method described above, although no p-values will be calculated in these analyses.

For the analysis of the primary efficacy endpoint in the full study, a 2-sided p-value < 5% will be considered statistically significant.

Analysis of secondary and exploratory endpoints in full study

Secondary and exploratory endpoints defined in section 8.6.2 and 8.6.3 will be analysed using the same approach described for the primary endpoint, giving hazard ratios and 95% confidence intervals; however, no p-values will be calculated in these analyses. Where no "time to event" data are available, binomial regression will be used.

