## 8.6.2 Secondary endpoint

- Time from randomisation to the first confirmed event of the individual components of the primary composite endpoint *i.e.* CV mortality, nonfatal myocardial infarction or nonfatal stroke.
- Time to any cause of death (supplied by Office of National Statistics)
- Time to first non-melanoma cancer diagnosis (supplied by National Cancer Registry)
- Time to death due to a non-melanoma cancer cause according to primary / underlying cause of death on death certificate (supplied by the Office of National Statistics)
- Physician diagnosed T2DM
- Participant satisfaction with treatment (adapted DTSQ) annually from randomisation and additionally at four months post-randomisation in the feasibility phase.
- Functional status (SF-8) annually from randomisation and additionally at four months post-randomisation in the feasibility phase.
- Health utility (EuroQol EQ-5D) annually from randomisation and additionally at four months post-randomisation in the feasibility phase.

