# 8.6.3 Exploratory endpoints

•Time from randomisation to

oConfirmed hospital admission for congestive heart failure oConfirmed hospitalisation for unstable angina

- oConfirmed coronary, cerebrovascular or peripheral revascularization
- Medical resource utilisation during the study (e.g. hospitalisations, outpatient physician visits, medication use) as measured by participant / GP questionnaires

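### Section 15.1 assigns Cox or binomial regression to repeated questionnaire scores and resource-use volumes, which neither method fits; SF-8 and treatment satisfaction have no suitable method anywhere in the protocol

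*Protocol*

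**What the plan says.** Protocol section 15.1 states one rule by explicit reference to the endpoint lists: "Secondary and exploratory endpoints defined in section 8.6.2 and 8.6.3 will be analysed using the same approach described for the primary endpoint". The output is to be hazard ratios with 95% confidence intervals and no p-values. The only alternative is that where no time-to-event "data are available, binomial regression will be used".

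The lists it points to contain more than events. Section 8.6.2 includes:

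- "Participant satisfaction with treatment (adapted DTSQ) annually from randomisation"
- "Functional status (SF-8) annually from randomisation"
- "Health utility (EuroQol EQ-5D) annually from randomisation"

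Each has an additional four-month measurement in the feasibility phase. Section 8.6.3 includes "Medical resource utilisation during the study (e.g. hospitalisations, outpatient physician visits, medication use) as measured by participant / GP questionnaires".

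Two other places bear on the point. Section 15.8 plans a health economic analysis that costs the reported resource use, takes QALYs as one effect measure, and reports group means, mean differences and their uncertainty. Section 15.6 leaves the details of the full-study analyses to a SAP that is still to be written.

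**The concern.** A score measured every year is neither a time to event nor a binary outcome. To use binomial regression the analyst must first turn each score into a yes/no variable, and the protocol defines no threshold for any of the three instruments. The result would depend on a cut chosen later. It would discard information within each score and would not give the quantity a reader expects, namely a mean difference in function, satisfaction or utility.

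Resource use raises a related problem. Hospitalisations and visits are counts, and the trial is event-driven (section 8.4) with recruitment over about two years (section 8.3), so participants are observed for different lengths of time. A binary analysis reduces the volume to any versus none, and section 15.1 says nothing about unequal exposure.

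At stake are three of the eight secondary endpoints and one exploratory endpoint. EQ-5D would also be summarised in two unrelated ways: as a binary effect under 15.1 and as mean QALYs under 15.8.

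**Working it through.** **Figures in the protocol.** The rule in 15.1 carries no figure of its own. The one powered figure is the primary-endpoint target of 1,046 events (section 15.3: 17% relative risk reduction, 85% power, p = 0.05; two-sided in 15.1). It reproduces at a hazard ratio of 0.83 with 1:1 allocation:

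- Schoenfeld: 4 × (1.960 + 1.036)² / (ln 0.83)² ≈ 1,035 events.
- Freedman: (1.960 + 1.036)² × (1.83 / 0.17)² ≈ 1,041 events.

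Both are within 3% of 1,046. Neither uses the secondary endpoints, so the concern does not touch the sample size.

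**Matching the rule to the endpoints.**

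| Endpoint | Type of data | Method under 15.1 | Suitable method elsewhere |
|---|---|---|---|
| Primary components, deaths, cancer, heart failure, unstable angina, revascularisation | Time to event | Cox: fits | Not needed |
| Physician-diagnosed T2DM | Event | Cox if dates exist, otherwise binomial: fits | Not needed |
| EQ-5D | Annual score, baseline collected | Binomial: does not fit | Partly, as QALYs in 15.8 |
| Resource use | Counts or volumes | Binomial: does not fit | Partly, as costs in 15.8 |
| SF-8 | Annual score, no baseline | Binomial: does not fit | None |
| Adapted DTSQ | Annual score, no baseline | Binomial: does not fit | None |

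The baseline entries come from section 11.2 and Appendix 1, which schedule EQ-5D at baseline but not SF-8 or satisfaction.

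**Illustrative size of the loss.** The protocol gives no standard deviation, distribution, cut-off or correlation, so the following are assumptions and not estimates for this trial.

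1. Suppose a score is normal and is split so that a proportion p lies above the cut c, where c is the (1 − p) quantile. The efficiency of the binary comparison relative to comparing means is φ(c)² / [p(1 − p)].
   - p = 0.5: 0.3989² / 0.25 = 2/π = 0.64
   - p = 0.3: 0.58
   - p = 0.2: 0.49
   - p = 0.1: 0.34
2. If only one time point were used, the gain from repetition would also be forgone. The variance of the mean of five annual scores relative to one score is (1 + 4ρ)/5. That is 0.60 at an assumed ρ = 0.5 and 0.76 at ρ = 0.7.

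**What this means for precision.** Take 12,898 × (1 − 0.16) = 10,834 participants, assuming the 16% loss in section 15.3 also applies to questionnaires and that each person gives one score. The 95% interval for a mean difference then has half-width 1.96 × √(4 / 10,834) = 0.038 SD. At 64% efficiency the equivalent is 0.038 / √0.64 ≈ 0.047 SD. Precision stays high in either case. The main defect is therefore an undefined cut and the wrong summary measure, with lost power secondary.

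**The case against.** The strongest defence is that the paragraph was meant only for event endpoints. It promises hazard ratios, and the binomial fallback suits T2DM, which 8.6.2 lists without a time element. The absence of any responder cut-off suggests that nobody intended to dichotomise the scores. On that reading 15.1 is silent on them and the SAP will supply the method.

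This does not succeed. The sentence names 8.6.2 and 8.6.3 as a whole and makes no exception. Section 15.1 defers to the SAP expressly for the graphical checks of proportional hazards and the alternatives if that assumption fails, but not for these endpoints. A SAP with a suitable longitudinal model would depart from the protocol, not add detail to it.

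Other parts of the defence stand, and they limit stronger readings that a reader might infer:

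- *That these objectives cannot be answered.* The scores are collected annually and at the end of the study, so a corrected analysis remains possible before unblinding.
- *That the trial will report no mean difference in utility.* Section 15.8 commits to mean differences in effects, including QALYs, and in costs. It does so for cost-effectiveness, not for the stand-alone endpoints, so the coverage is partial.
- *That binomial regression must ignore baseline and repetition.* It accepts covariates and can be extended to repeated outcomes. The protocol does not say how it would be implemented.
- *That the missing SF-8 baseline or the T2DM wording is part of the error.* Randomisation gives an unbiased SF-8 comparison without a baseline, so adding one is a design preference. Section 15.1 already applies Cox regression wherever time-to-event data exist.

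**Conclusion.** The rule is wrong as written for adapted DTSQ, SF-8, EQ-5D and resource use. For SF-8 and treatment satisfaction the protocol offers no suitable method at all. For EQ-5D and resource use, section 15.8 provides a partial substitute.

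The consequence is moderate. The endpoints are secondary or exploratory and carry no p-values, and the primary analysis and sample size are unaffected. The mismatch between rule and endpoints follows from the text alone. The 64% figure does not: it assumes a normal score cut at its median, and other cuts do worse. No trial-specific loss can be calculated from the protocol. This should be corrected before the SAP is finalised, but it does not threaten the main result.

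**What to change.** Replace the rule in 15.1 with one that separates the endpoint types:

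- **Event endpoints.** Keep Cox regression, with binomial regression where only occurrence is known.
- **Adapted DTSQ, SF-8 and EQ-5D.** Use a linear mixed model for repeated annual measures with treatment, visit and their interaction, reporting mean differences with 95% confidence intervals. Adjust EQ-5D for its baseline value; it is the only one of the three collected then.
- **Deaths and missing questionnaires.** State how each is handled. A mean among surviving responders would not correspond to the QALYs in 15.8, so the text should say which quantity each analysis estimates.
- **Resource use.** Use a count model with a log follow-up offset for the components that are counts, or cross-refer to 15.8.

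The cost is protocol and SAP wording. No new data, visits or participants are needed.

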#### 15.2 Interim analyses

The analysis of the feasibility phase will be descriptive; no p-values will be calculated. The analysis will be conducted after 250 participants have been randomised. The interim analysis will include presentation of the following information, separately by randomised group:

- •Number and percentage of individuals recruited via each of the 3 recruitment strategies.
- •Summaries of baseline characteristics of recruited participants; these summaries will be means and standard deviations for continuous variables with a reasonably symmetric distribution, medians and interquartile ranges for continuous variables with a skewed distribution, and frequencies and percentages for categorical variables.
- •Baseline estimate of future cardiovascular risk using Framingham risk equations
- •Compliance with study medication.
- •Creatinine and HbA1c values at 0, 3 and 6 months; B12 and LFT values at 0 and 6 months

Success of the feasibility phase, e.g. examination of the parameters outlined above, will determine if we proceed to the full study (subject to appropriate funding). It is anticipated that the full study will commence no more than 2.5 years (30 months) after the start of the feasibility phase. This allows sufficient time for analysis to test the model is viable and to roll out the study to the additional regions.

#### 15.3 Number of participants to be enrolled

For the feasibility phase: It is not appropriate to estimate power in a feasibility phase when the aims are to assess study feasibility rather than to demonstrate a treatment effect. However, it is possible to determine the precision with which certain parameters can be estimated, based on a sample size of 250 individuals:

Expected recruitment rate via vascular checks programme: based on data from ADDITION-Leicester, this was 20%. With 250 individuals the 95% confidence interval around an estimate of 20% would be from 15% to 26%. However, this trial required an OGTT, so may be an underestimate of what could be expected in GLINT (which does not require fasting or an OGTT). If instead the recruitment rate were 50%, the 95% confidence interval around this estimate would be from 44% to 56%.

Expected recruitment rate directly from participating general practices: based on data from ADDITION-Cambridge, this was 74%. With 250 individuals the 95% confidence interval around an estimate of 74% would be from 68% to 79%.

Expected modelled risk: based on data from EPIC-Norfolk, this was 2.2% per year. With 250 individuals the 95% confidence interval around an estimate of 2.2% would be from 0.9% to 5.2%.

Expected adherence to IMP: based on data from the DPP, this was 80%. With 250 individuals the 95% confidence interval around an estimate of 80% would be from 74% to 85%.

For the full study: EPIC-Norfolk data suggests that 10% of individuals screened by the NHS checks programme will have a CVD risk >20%, an HbA1c of 36.6 and 47.5mmol/mol, and an annual CVD event rate of 2.2%. We have considered the estimated event rate in our study in light of currently declining CVD rates. The estimate from EPIC-Norfolk is relatively low as the Standardised Mortality Ratio in this region is 94 and the cohort appears to exhibit the 'healthy volunteer effect'. As GLINT will recruit a significant proportion of people from black and minority ethnic groups and individuals from a part of the UK with higher CVD event rates (for example Scotland for the full study and East Midlands for the feasibility study), we believe our estimate is conservative and protects this study from a low event rate due to a secular decline in CVD. If 25% agree to participate, and 16% are lost to follow-up, we require 1,046 confirmed primary events to detect a treatment difference. We therefore need 515,920 individuals to be screened and 12,898 participants randomised to detect a 17% CVD relative risk reduction (85% power, p=0.05). Treatment effect is estimated from observed CVD risk reductions in T2DM (15-30% [6, 26, 27]) and expected CVD risk reductions (9-13%) due to changes in HbA1c, BMI, lipids, and blood pressure among people with non-diabetic hyperglycaemia.[23] A lesser treatment effect might become unattractive from clinical and health economic perspectives. For example, a relative risk reduction of less than 17% would mean that more than 59 individuals would need to be treated for 5-years to prevent one CVD event.

#### 15.4 Criteria for the premature termination of the study

The stopping guideline to be included in the IDMC charter will detail when they might recommend premature termination of the study to the Trial Steering Committee. The IDMC charter will be filed in the TMF. The specific roles of the IDMC is to perform an interim review of the study's progress including updated figures on recruitment, data quality, adherence to protocol treatment and follow-up, and main outcomes and safety data.

#### 15.5 Procedure to account for missing or spurious data

In the analysis of the efficacy endpoints of the full study, participants who are lost to follow-up will be censored at their last known follow-up time.

# 15.6 Procedures for reporting any deviation(s) from the original statistical plan

A Statistical Analysis Plan describing the details of the proposed analyses of the full study will be written and reviewed by members of the MRC Biostatistics Hub in Trials Methodology Research based in Cambridge as well as the TSC, before publication on the study and ISRCTN websites prior to unblinding. Any subsequent deviations from this plan will be reported in the publication describing the results from the study.

